## LIST OF ABBREVIATIONS

AE	Adverse Event
AIDS	Acquired Immunodeficiency Syndrome
ALT	Alanine aminotransferase
AST	Aspartate aminotransferase
ART	Antiretroviral Therapy
CoE-T	Center of Excellence for Transgender Health
CFR	Code of Federal Regulations
CRF	Case Report Form
DMC	Data Monitoring Committee
DOT	Directly Observed Therapy
DSMB	Data Safety Monitoring Board
FDA	Food and Drug Administration
FTC	Emtricitabine
FTC/TDF	Emtricitabine/ Tenofovir disoproxil fumarate
GCP	Good Clinical Practice
HIPAA	Health Insurance Portability and Accountability Act of 1996
HIV	Human Immunodeficiency Virus
HT	Hormone Therapy
ICF	Informed Consent Form
ICH	International Conference on Harmonisation
IEC	Independent Ethics Committee
iPrEx	iniciativa Profilaxis Pre-Exposición
IRB	Institutional Review Board
MSM	Men who have Sex with Men
PI	Principal Investigator
PK	Pharmacokinetic
PrEP	Pre-Exposure Prophylaxis
RCT	randomized controlled trial
SAE	Serious Adverse Event
TDF	Tenofovir disoproxil fumarate
TFV-DP	Tenofovir diphosphate
UCSF	University of California, San Francisco
ULN	upper limit of normal

## PROTOCOL SYNOPSIS

TITLE	I-BrEATHe - Interactions BEtween Antiretrovirals And Transgender Hormones.
SPONSOR	[name] and [name]
FUNDING ORGANIZATION	University of California Office of the President via the California HIV/AIDS Research Program
NUMBER OF SITES	1
RATIONALE	
Drug concentrations after receipt of oral Truvada Pre Exposure Prophylaxis (or PrEP) appeared to be lower in transgender women compared to Men who Have Sex with Men (MSM) in the iPrEx study. Reasons for the lower drug concentrations may be behavioral or biomedical, or a combination of both. There are few to no studies which investigate the potential drug to drug interactions between the components of Truvada (emtricitabine or FTC and tenofovir disoproxil fumarate or TDF) and feminizing hormones. In addition, no PrEP studies have ever included transgender men; therefore no knowledge exists on the potential interactions between FTC/TDF and masculinizing hormones.
 
The pharmacokinetic study, using directly observed therapy (DOT), is designed to address the question whether feminizing or masculinizing hormones affect FTC/TDF levels in transgender women or transgender men respectively.

STUDY DESIGN	This is a pharmacokinetic study
PRIMARY OBJECTIVE	Assess pharmacokinetic drug-drug interactions between tenofovir disoproxil fumarate/emtricitabine (TDF/FTC) and cross-sex hormone therapy.
SECONDARY OBJECTIVES	Assess Adverse Events related to TDF/FTC in transgender men and women and compare to historical controls in non transgender MSM
NUMBER OF PARTICIPANTS	48 (24 transgender women and 24 transgender men)
PARTICIPANT SELECTION CRITERIA	
Inclusion Criteria:
 
All subjects:
 
 
• HIV antibody seronegative (negative HIV rapid test),
 
• 18 years or older,
 
• Has a smart phone with access to two-way video call capability,
 
• Willingness to be contacted for a short call every day for 4 weeks,
 

	

• Adequate renal function (creatinine clearance <math>\geq 60</math> ml/min estimated by the Cockcroft Creatinine Clearance Formula),

• Provides written informed consent,

 
For Transgender women:
 

• Assigned male sex at birth, and self-reported current gender identity as “woman” or “transgender women”, or other trans-feminine spectrum identity,

• Current feminizing Hormone Therapy (HT) use for at least 6 months

 
For Transgender men:
 

• Assigned female sex at birth, and self-reported current gender identity as “man” or “transgender man”, or other trans-masculine spectrum identity,

• Current masculinizing Hormone Therapy (HT) use for at least 6 months with testosterone.

 
Exclusion Criteria:
 

• Expects to change or discontinue current HT use during the 4 weeks study period,

• Signs of symptoms of acute viral syndrome,

• Use of FTC or TDF in the past 90 days

• Receiving ongoing therapy with any of the following: ART, including nucleoside analogs, non-nucleoside reverse transcriptase inhibitors, protease inhibitors or investigational antiretroviral agents, interferon (alpha, beta, or gamma) or interleukin (e.g., IL-2) therapy, aminoglycoside antibiotics, amphotericin B, cidofovir, systemic chemotherapeutic agents, other agents with significant nephrotoxic potential, other agents that may inhibit or compete for elimination via active renal tubular secretion (e.g., probenecid), and/or other investigational agents

• Renal insufficiency documented as Creatinine Clearance <math>< 60</math> ml/min

• For masculine-spectrum identifying persons, positive pregnancy test at screening

• At enrollment, has any other condition that, based on the opinion of the investigator or designee, would preclude provision of informed consent; make participation in the study

--	---

	unsafe; complicate interpretation of study outcome data; or otherwise interfere with achieving the study objectives.
TEST PRODUCT, DOSE, AND ROUTE OF ADMINISTRATION	FDA approved Truvada (one tablet containing 200 mg of emtricitabine or FTC and 300 mg of tenofovir disoproxil fumarate or TDF) once daily taken orally with or without food. Gilead Sciences will dispense medication to through their FDA approved commercial packaging of 30 tablets per bottle with an included desiccant.
CONTROL PRODUCT, DOSE AND ROUTE OF ADMINISTRATION	N/A
DURATION OF PARTICIPANT PARTICIPATION AND DURATION OF STUDY	
Participants will be on study for up to 56 days
 
Screening: up to 28 days
 
Treatment: 4 weeks or 28 days (participants come to clinic weekly and DOT via video calls)
 
Follow-up: n/a
 
The total duration of the study is expected to be 7-9 months: 1-3 months for participant recruitment and 6 for final participant follow-up.

CONCOMITANT MEDICATIONS	
Allowed:
 
Testosterone, estradiol, spironolactone,
 
Prohibited:
 
ART, including nucleoside analogs, non-nucleoside reverse transcriptase inhibitors, protease inhibitors or investigational antiretroviral agents, interferon (alpha, beta, or gamma) or interleukin (e.g., IL-2) therapy, aminoglycoside antibiotics, amphotericin B, cidofovir, systemic chemotherapeutic agents, other agents with significant nephrotoxic potential, other agents that may inhibit or compete for elimination via active renal tubular secretion (e.g., probenecid), and/or other investigational agents

EFFICACY EVALUATIONS	N/A
PRIMARY ENDPOINT	Concentrations of FTC triphosphate and tenofovir diphosphate (TFV-DP) in Dried Blood Spots (DBS)
SECONDARY ENDPOINTS	N/A
OTHER EVALUATIONS	N/A

SAFETY EVALUATIONS	Incidence of adverse events ( AEs will be collected as part of the weekly visit if participants report AEs )
PLANNED INTERIM ANALYSES	N/A
STATISTICS Primary Analysis Plan	We will compare levels of Tenofovir DiPhosphate (TFV-DP), the phosphorylated active tenofovir molecule in dried blood spots and rates of adverse events between trans men and trans women and a group of MSM historical controls from the iPrEx OLE study. We will compare log transformed TFV-DP levels using a linear mixed effects model with factors for group (trans men v. trans women v. MSM) and times (1, 2, 3 and 4 weeks after initiation) and their interaction with an unstructured covariance across visits and test for differences at between groups at each time point. If values appear to violate the normal distribution, we will obtain p-values and confidence intervals using the bootstrap. All p-values will be two-sided with p-value < 0.05 considered statistically significant. Adverse events will be compared using the Fisher exact test.
Rationale for Number of Participants	A sample size of 48 (24 trans women and 24 trans men) allows detection of a difference of 0.52 log difference (1.68 fold difference) in TFV-DP from dried blood spots with 81% power on a two-sided 0.05 level test at any time point between our trans participants and MSM historical controls. A difference of 0.70 log (2.0 fold difference) can be detected between either group (trans men or women), and MSM historical controls with 80% power on a two-sided 0.05 level test.

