## 2.2 Overview of Clinical Studies

There have been a large number of trials conducted with Truvada PrEP, including several demonstration projects. While there is no evidence to suggest that TDF/FTC interacts with commonly used feminizing or masculinizing hormone regimens, and evidence from studies of ARV interactions with hormonal contraceptives have been reassuring, no direct study of these interactions has been conducted to date.

Our team led the only trans-specific sub analysis to date of the iPrEx randomized controlled trial (RCT) data as well as the open label extension (OLE) study, which included periodic dried blood spot (DBS) drug level monitoring [2]. In iPrEx, gender identity data was not collected using current best practices (“two-step” method [5]), making the identification of transgender participants in this multinational, multicultural and multilingual trial difficult. As all iPrEx participants had been assigned male sex at birth, a transgender subgroup of 339/2499 participants (14% of overall sample) was constructed comprised of the 29 (1%) who identified as women, 296 (12%) who identified as “trans”, and 14 (1%) who reported use of feminizing hormones. None had undergone gender affirming genital surgery. Compared with MSM, transgender women more frequently reported transactional sex, receptive anal intercourse without a condom, or more than 5 partners in the past 3 months. Excluding those with a male identity who also used feminizing hormones, trans- and woman-identified participants were less likely to have TDF levels detected on random testing in the RCT (OR=0.39, 95% CI = 0.16 to 0.96, p=0.04). While there was no effectiveness of PrEP for transgender women on an intention-to-treat basis, none of the transgender participants who seroconverted had detectible drug levels at the time of HIV diagnosis. In comparison to MSM in the OLE, transgender participants had less time with protective drug concentrations (17% vs 35%, p<0.001) and were less likely to have concentrations indicating > 3 tablets/week (OR 0.71, 95% CI 0.49 to 1.03, p=0.07). Of the two transgender women who seroconverted during the OLE, both had drug levels below 350 fmol/punch in DBS, the level associated use of 2 tablets per week at the time of seroconversion. The lower concentrations were more likely if the transgender women used feminizing hormones.

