### 3.1 Risk / Benefit Assessment

Oral Truvada for PrEP has been FDA approved since 2012. At this time, there is plentiful evidence to support the use of daily oral FTC/TDF in HIV-1-uninfected heterosexual biological men and women, and men who have sex with men for HIV prevention [12]. The toxicity and tolerability of daily oral FTC/TDF in HIV-uninfected individuals have been established. Side effects that may arise in the first weeks of PrEP use -- nausea, abdominal cramping, vomiting, dizziness, headache, and fatigue usually go away without treatment interruption (see Truvada Prescribing information for more details). Known potential risks can be effectively managed by experienced PrEP providers. Participants enrolled in this study will be provided Truvada for PrEP within the confines of an established PrEP clinic, and will benefit from the expertise of trained staff. Individuals who may be susceptible to the possible nephrotoxic effect of FTC/TDF as determined by the measure of creatinine clearance (see exclusion criteria) will not be enrolled in the study. Long term effect of Truvada use (such as bone density loss or kidney dysfunction) are unlikely to occur over the course of this short study in otherwise healthy participants [13-15]. Participants will be seen weekly by a clinician, and any adverse event immediately addressed, in addition participants will be interacting daily with study staff via phone, providing an opportunity to address any questions or concerns. Moreover, the daily interactions with study staff will provide support for adherence. Concerns about risks of combining gender-affirming hormone therapy and PrEP will be alleviated by trained providers with expertise in the management of both antiretroviral and hormone

therapy. Guidelines for these matters will be provided by the UCSF Center of Excellence for Transgender Health (CoE-T).

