## 7 PARTICIPANT SELECTION

### 7.1 Study Population

I-BrEATHe is a sub study of the TRIUMPH study with an anticipated overall cohort of 188 transgender participants. Volunteers who are participants in the larger TRIUMPH project may be recruited to participate in this sub study, however the I-BrEATHe sub study may also enroll volunteers outside of the TRIUMH study.

Up to 48 volunteers who meet the inclusion and exclusion criteria will be eligible for participation.

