### 7.3 Exclusion Criteria

- Expects to change or discontinue current HT use during the 4 weeks study period,
- Signs of symptoms of acute viral syndrome,
- Use of FTC or TDF in the past 90 days
- Receiving ongoing therapy with any of the following:

*ART, including nucleoside analogs, non-nucleoside reverse transcriptase inhibitors, protease inhibitors or investigational antiretroviral agents interferon (alpha, beta, or gamma) or interleukin (e.g., IL-2) therapy, aminoglycoside antibiotics, amphotericin B, cidofovir, systemic chemotherapeutic agents, other agents with significant nephrotoxic potential, other agents that may inhibit or compete for elimination via active renal tubular secretion (e.g., probenecid), and/or other investigational agents*

- Renal insufficiency documented as Creatinine Clearance < 60 ml/min
- For masculine-spectrum identifying persons, positive pregnancy test at screening
- At enrollment, has any other condition or factor that, based on the opinion of the investigator or designee, would preclude provision of informed consent; make participation in the study unsafe; complicate interpretation of study outcome data; or otherwise interfere with achieving the study objectives.

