### **15.3 Analysis of Primary Endpoint**

We will compare levels of TFV-DP in dried blood spots and rates of adverse events between trans men and trans women and a group of MSM historical controls from the iPrEx OLE study. We will compare log transformed TFV-DP levels using a linear mixed effects model with factors for group (trans men v. trans women v. MSM) and times (1, 2, 3 and 4 weeks after initiation) and their interaction with an unstructured covariance across visits and test for differences at between groups at each time point. If values appear to violate the normal distribution, we will obtain p-values and confidence intervals using the bootstrap. All p-values will be two-sided with p-value < 0.05 considered statistically significant. Adverse events will be compared using the Fisher exact test.

Adverse event rates will be coded by body system and MedDra classification term. Adverse events will be tabulated and will include the number of patients for whom the event occurred, the rate of occurrence, and the severity and relationship to study drug.

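### The MSM comparator has no stated drug-history, renal, co-medication or dosing rule, although trans participants are held to all four; the resulting biases oppose each other and the net direction is unknown

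*Combined protocol and SAP*

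**What the plan says.** **Trans participants.** The Protocol Synopsis and section 7.3 exclude anyone with "Use of FTC or TDF in the past 90 days", anyone with "Renal insufficiency documented as Creatinine Clearance < 60 ml/min", and anyone taking "other agents that may inhibit or compete for elimination via active renal tubular secretion (e.g., probenecid". Section 7.1 ties these criteria to the people entering this study: "Up to 48 volunteers who meet the inclusion and exclusion criteria will be eligible for participation". Section 9.6 sets daily observed dosing and removes a participant who misses two or more doses. Section 15.1 limits the pharmacokinetic analysis to those who received all doses.

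**MSM comparator.** The Synopsis and section 15.3 call it "a group of MSM historical controls from the iPrEx OLE study" and say no more about who is in it. Section 2 describes iPrEx as a trial of daily oral Truvada. Section 2.2 refers to "the iPrEx randomized controlled trial (RCT) data as well as the open label extension (OLE) study", and reports that MSM in the extension had protective concentrations 35% of the time. Section 3 describes the comparison data differently, as previously acquired MSM dried-blood-spot levels from references 9 to 11. By its title, reference 10 is a directly observed dosing study in healthy volunteers.

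**Model.** Section 15.3 puts all three groups on one clock, "times (1, 2, 3 and 4 weeks after initiation"), and tests group differences at each time point. Initiation is not defined for controls. The primary objective (section 4.1) asks whether concentrations are lower in trans participants than in MSM.

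**The concern.** The trans groups are new users by design. The control group comes from the extension of a trial of the same drug, so some of its members may have taken FTC/TDF in the randomized phase. Nothing in the plan stops such a person being counted as a control at week 1 with earlier drug still present. That would raise the control level and make trans levels look lower, which is the direction the objective asks about. The renal and co-medication rules raise the same issue, because each keeps out people likely to have higher levels and neither is stated for controls.

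Adverse events are affected too. Section 3.1 speaks of "Side effects that may arise in the first weeks of PrEP use" that usually resolve. Controls already past that phase could report fewer events, and trans participants would then seem to tolerate the drug worse.

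The dosing rules are also one-sided, with the opposite effect on concentrations. The documents do not describe dosing in the extension as observed. Controls who skip doses have lower levels, which makes trans levels look high and could hide a real interaction.

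**Working it through.** **1. The plan's own figures.** Section 15.4 gives 0.52 log (1.68-fold) with 81% power for 48 trans participants against controls, and 0.70 log (2.0-fold) with 80% power for 24. The fold changes check: exp(0.52) = 1.68 and exp(0.70) = 2.01. The power cannot be verified independently, because neither the SD nor the number of controls is stated. Solving the two statements together:

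- SE for 48 = 0.52/(1.960 + 0.878) = 0.183
- SE for 24 = 0.70/(1.960 + 0.842) = 0.250
- SD² = 48 × (0.250² − 0.183²) ≈ 1.385 before rounding of the SEs, so SD ≈ 1.18
- controls = 1/(0.183²/1.385 − 1/48) ≈ 293 before rounding

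This is a back-solve, not a check. With a 2-point tolerance on the second power figure, about 150 to 1000 controls fit (SD about 1.10 to 1.24).

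**2. Carry-over in controls.** The documents give no TFV-DP half-life *h*, no residual level *R* at the control start date (as a fraction of steady state) and no share of pre-exposed controls. I assume h = 10 to 25 days and R = 10 to 25%. With first-order accumulation and k = 2^(−7w/h) at week w, a pre-exposed control divided by a new user is 1 + R·k/(1 − k).

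| Week | Lowest (h = 10, R = 0.10) | Highest (h = 25, R = 0.25) |
|---|---|---|
| 1 | 1 + 0.10 × 0.616/0.384 = 1.16 | 1 + 0.25 × 0.824/0.176 = 2.17 |
| 2 | 1.06 | 1.53 |
| 4 | 1.02 | 1.21 |

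If half the controls are pre-exposed, the control geometric mean shifts by the square root of the ratio: 1.08 to 1.47-fold at week 1 and 1.01 to 1.10-fold at week 4.

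**3. Effect on the test if there is no interaction.** For a log shift d, the chance of p < 0.05 is Φ(d/SE − 1.96) + Φ(−d/SE − 1.96). Take a 1.33-fold shift (week 1, h = 17, R = 0.25, half exposed), so d = 0.285:

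- 24 against controls, SE 0.250: 21%
- 48 against controls, SE 0.183: 34%

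At the week-4 maximum of 1.10-fold with SE 0.250, the chance of a significantly lower result in trans participants is about 6%, against 2.5% nominal.

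**4. Unobserved dosing in controls.** If steady partial dosing scales the level by doses taken out of 7, the log shift in controls is ln(6/7) = −0.15, ln(5/7) = −0.34 or ln(4/7) = −0.56, at every week.

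**5. Both together.** Suppose controls take 5 of 7 doses and half are pre-exposed with R = 0.25. The control geometric mean, relative to fully dosed new users, is √[(5/7) × (5/7 + R·k/(1 − k))].

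| h (days) | Week 1 | Week 2 | Week 4 |
|---|---|---|---|
| 10 | 0.89 | 0.79 | 0.74 |
| 17 | 1.03 | 0.86 | 0.77 |
| 25 | 1.16 | 0.94 | 0.81 |

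The sign depends on inputs that the plan does not give, and at the longer half-lives it changes between week 1 and week 4.

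**The case against.** A reader might infer that the controls are unscreened and that trans levels will therefore look falsely low. The documents support neither step.

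- **Selection is undescribed, which is not the same as absent.** The extension's eligibility rules, and any gap after the randomized phase, lie outside these documents. The shared clock of weeks after initiation can be read as meaning new starters. If all controls stopped FTC/TDF long before, carry-over is near zero.
- **The direction is not established.** Observed dosing, removal for missed doses and the all-doses analysis set apply only to trans participants. The 35% figure in section 2.2 makes imperfect dosing among extension MSM a real prospect.
- **The source is not settled.** If the observed-dosing data cited in section 3 are used, the carry-over argument need not apply.
- **The sizes rest on stacked assumptions.** Residuals of 10 to 25% at these half-lives mean stopping about 20 to 83 days before the start date.
- **The 90-day rule is not itself an error,** and section 15 promises a detailed SAP before the final analysis.

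All of this stands as a limit on the claim. It does not supply the missing rule. Carry-over is concentrated in the early weeks, whereas steady partial dosing acts at every week, so the two cannot be relied on to cancel in tests made week by week. Restricting controls to good adherers would not remove carry-over, and a drug-history filter alone would leave the dosing bias unopposed. For adverse events the two need not offset: if events rise with exposure, earlier use and lower adherence would both reduce control rates.

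**Conclusion.** The gap is real and lies in the definition of the comparator in the Synopsis, section 3 and section 15.3. Followed as written, the plan can admit controls with earlier FTC/TDF exposure and unverified dosing, and compare them with washed-out, observed, fully dosed trans participants. The carry-over component alone is worth 1.16 to 2.17-fold per pre-exposed control at week 1 and 1.02 to 1.21-fold at week 4, on assumed half-lives, residuals and exposure. The dosing component runs the other way and can be as large or larger by week 4. The net direction of the concentration bias cannot be known from the documents, and a claim that trans levels will look falsely low goes too far. Lower control adverse event rates are possible but cannot be quantified. This is a cheap improvement to the plan; it does not show that the result will be wrong.

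**What to change.** In the Synopsis and section 15.3, carried into the SAP before control data are analysed:

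1. Reconcile the control source with section 3, name the dataset, and state the number of controls and the SD used for sample size.
2. Define initiation for controls as the first dose after at least 90 days without FTC/TDF, counting active drug in the randomized phase. Undetectable TFV-DP at the start could serve as the alternative test.
3. Apply this trial's renal and co-medication exclusions to controls where data exist, and say where they do not.
4. Restrict the primary contrast, or at least a prespecified sensitivity analysis, to controls with observed or verified daily dosing. Make this change together with item 2, so that neither bias is left unopposed.
5. Use the same drug-history filter for the adverse event comparison.

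The cost is wording, a filter on control records, and some precision. With the back-solved SD² of 1.385, the per-group detectable log difference is 2.80 × √(1.385/24 + 1.385/n). That gives 0.70 (2.01-fold) at n = 293, 0.73 (2.07-fold) at 147 and 0.75 (2.12-fold) at 100. The number of controls that would pass the filters is unknown, so the team should count them before fixing the rule.
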